8.0 Statistical Methods

8.1 General Considerations

This protocol describes key safety and efficacy analyses of data collected as currently planned. A SAP will be developed based on the clinical protocol and eCRFs and finalized prior to unblinding of the study; it will include a detailed description of the statistical methodology including the treatment of missing data and the patient eligibility criteria. No database will be locked or analyses completed until the SAP has been approved. If differences occur between analyses of data described in the SAP and the current protocol, those found in the SAP will assume primacy.

Unless otherwise noted, continuous variables will be summarized using number of non-missing observations, mean, standard deviation, median, minimum, and maximum; categorical variables will be summarized using the frequency count and the percentage of patients in each category. In addition to the descriptive summaries, pertinent data listings will be provided.

All analyses will be performed using SAS[®] version 9.2 or higher, unless otherwise specified.

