8.7.3 Clinical Laboratory Evaluations

Summary statistics for each scheduled time point measured and mean changes from baseline to each time point (when applicable) will be presented for clinical laboratory results.

All laboratory evaluation summaries will include the patients in the Safety Population who have at least 1 postbaseline time point (for criteria based on postbaseline assessments) and with both a baseline and at least 1 postbaseline time point (for criteria evaluating changes from baseline).

Laboratory values will be reported in Système International units.

Laboratory test results will be assigned an L/N/H classification according to whether the value was below (L), within (N), or above (H) the laboratory parameter’s reference range. Comparisons will be based on 3×3 tables (shift tables) that, for a particular laboratory test, compare the baseline L/N/H classification to the highest and/or lowest L/N/H classification during the treatment period. Clinically important laboratory values based on prespecified criteria defined in the SAP will also be summarized.

Additionally, alanine aminotransferase, aspartate aminotransferase, bilirubin, and alkaline phosphatase will be presented in a separate listing, with $3 \times$ and $5 \times$ ULN flagged for alanine aminotransferase and aspartate aminotransferase; $2 \times$ ULN flagged for bilirubin, and $1.5 \times$ ULN flagged for alkaline phosphatase.

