6.2 Full Analysis Set (FAS)

The full analysis set is defined as all randomized patients who received at least 1 dose of study drug. Patients in the full analysis set will be analyzed according to their randomized treatment, regardless of the actual treatment received. The Full Analysis set will be used to analyze all efficacy endpoints.

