6.3 Safety population (Safety)

The safety analysis population is defined as all randomized patients who received at least 1 dose of study drug. Patients in the safety analysis population will be analyzed according to their actual treatment. The Safety Population will be used to analyze all safety endpoints.

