8 STATISTICAL METHODS

8.1 General statistical conventions

All statistical procedures will be completed using SAS version 9.2 or higher.

Unless otherwise noted, continuous variables will be summarized using descriptive statistics, including number of patients with non-missing observation (n), mean, median, standard deviation (SD), minimum (min) and maximum (max). Means and medians will be reported to one decimal place more than the raw data. Standard deviation will be reported to two more decimal places than the raw value. The minimum and maximum will be reported to the same decimal as the raw data.

Categorical variables will be summarized using the frequency count and the percentage of patients in each category. All percentages will be rounded to one decimal point. The number and percentage of patients will always be presented in the form XX (XX.X%) where the percentage is in parentheses. To ensure completeness, all summaries for categorical and discrete variables will include all categories, even if none of the patients in a particular category. Counts of zero in any category will be presented as “0”. Unless otherwise noted, for all percentages, the number of patients in the analysis population for the treatment group will be the denominator.

“Baseline” will be defined as per [section 7.1](#). For efficacy endpoints, “on-treatment” is defined as any assessment following the first dose of study drug and within 2 days from the last dose of study drug recorded in the patient diary. For safety endpoints (excluding adverse events), any assessment within 7 days after last dose of study drug will be deemed “on-treatment”. For all endpoints “End of treatment” (EOT), in summaries, will be represented by the last non-missing on-treatment value recorded up to and including the Week 12/Early Termination visit. Treatment emergence for adverse events is described in [section 8.7.1](#). Summaries will be presented across all scheduled visits and EOT unless stated otherwise. Only on-treatment data will be used in summaries and statistical analyses (with the exception of the Patient Global Impression of Change).

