- Change from baseline in itch-related quality of life at each scheduled post baseline week of the Treatment period, as assessed by the total score of the 5-D itch scale. Treatment differences between each CR845 dose group and placebo at each post baseline time points will be evaluated and presented (except week 12) using the MMRM fitted for the secondary efficacy analysis [section 8.6.3](#).
- The proportion of patients who either rate the degree of itching intensity as 'Not Present' or the direction of itching as 'Completely Resolved' over the past 2 weeks from the 5-D Itch Scale will be calculated at Week 12 and end of treatment. Treatment differences will be compared using a logistic regression model with terms for treatment group, baseline 5-D Itch Total Score and renal disease status. In addition, pairwise treatment differences will be tested using the Cochran-Mantel-Haenszel test, adjusting for strata (i.e renal disease status). An exact test of whether the common odds ratio across strata equals 1 will be used if the observed count in a particular cell is small (ie, <5).
- The proportion of patients with itching present at each body part will be presented at Week 12 and end of treatment along with the shift from baseline (Present or Not Present combinations). The presence of itching at each body part at end of treatment will be compared between treatments adjusting for strata (i.e renal disease status) and presence of itch at baseline (Present/Not Present). An exact test of whether the

Statistical Analysis Plan (SAP)

common odds ratio across strata equals 1 will be performed.

- Change from baseline in itch-related quality-of-life at each week of the Treatment period, as assessed by the total score of the Skindex-10 Scale. Treatment differences between each CR845 dose group and placebo at each scheduled post baseline time points will be evaluated and presented (except week 12) using the same MMRM fitted for the secondary efficacy analysis [section 8.6.3](#).

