8.7.2 Clinical laboratory evaluations

Blood samples for clinical laboratory tests, including hematology, serum chemistry and serum pregnancy will be collected during screening and day 1 before study drug administration, on week 6 and week 12 (end of treatment).

All clinical laboratory data will be reported in Système International units.

Summary statistics for each scheduled time point measured and mean changes from baseline to each time point will be presented for hematology and serum chemistry laboratory results. The baseline value is defined as the last observation prior to or on the date of the first dose of study drug whether scheduled or unscheduled (see [section 7.1](#)).

Hematology and serum chemistry laboratory test results will be assigned as Low (L), Normal (N) or High (H) classification according to whether the value was below (L), within (N), or above (H) the laboratory parameter’s reference range.

Statistical Analysis Plan (SAP)

Comparisons will be based on 3×3 tables (shift tables) that, for a particular laboratory test, compare the baseline L/N/H classification to the highest and/or lowest L/N/H classification during the treatment period.

Clinically important laboratory values based on the below specified criteria will also be summarized.

- Alanine aminotransferase (ALT), aspartate aminotransferase (AST),
 - $>3 \times$ ULN
 - $>5 \times$ ULN
 - ALT $>3\times$ ULN or AST $>3\times$ ULN
- Alkaline phosphatase (ALP)
 - $>1.5 \times$ ULN
- Total Bilirubin (TBILI)
 - $>2 \times$ ULN
- AST and Total Bilirubin
 - AST $>3\times$ ULN and TBILI $>2\times$ ULN
- ALT and Total Bilirubin
 - ALT $>3\times$ ULN and TBILI $>2\times$ ULN
- AST or ALT and Total Bilirubin
 - AST or ALT $>3\times$ ULN and TBILI $>2\times$ ULN

A summary of treatment emergent sodium findings will also be provided, categorizing results into those <146 mmol/L, $146 - 150$ mmol/L, and >150 mmol/L at the 6 and 12 week assessments. An additional summary will present these categories for subjects over the full study period presenting the highest category attained (at any on-treatment assessment) and sustained (at any on-treatment assessment and all subsequent on-treatment assessments); this analysis will include both scheduled and unscheduled laboratory test results.

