8.7.3 Vital signs

Vital sign parameters include systolic blood pressure (SBP), diastolic blood pressure (DBP), body temperature and heart rate. For each scheduled timepoint, descriptive summary statistics will be calculated for both the actual and the change from baseline values for all

Statistical Analysis Plan (SAP)

vital sign parameters. The baseline value is defined as the last observation prior to or on the date of the first dose of study drug whether scheduled or unscheduled (see [section 7.1](#)).

Clinically notable vital signs will be identified based on the criteria below. For each vital sign parameter, the number and percentage of subjects with at least 1 notable value will be tabulated by week and overall for Treatment period. This analysis will include results from both scheduled and unscheduled assessments.

Vital Sign Parameter	Value
Systolic blood pressure	≥ 180 mm Hg
	≤ 90 mm Hg
Diastolic blood pressure	≥ 100 mm Hg
	≤ 60 mm Hg
Heart rate	>130 bpm
	<55 bpm

All vital signs will be listed in patient listings, including visit and collection date/time, and will be sorted by patient identifier and date/time of assessment.

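### The default denominator in SAP 8.1 understates every category percentage in the by-visit sodium, vital-sign and itch tables by the fraction of patients not assessed

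*SAP*

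**What the plan says.** The general rule is in SAP 8.1: "Unless otherwise noted, for all percentages, the number of patients in the analysis population for the treatment group will be the denominator". Both populations that it refers to need only a single dose, with no post-baseline assessment. For safety tables, "The safety analysis population is defined as all randomized patients who received at least 1 dose of study drug" (SAP 6.3). For efficacy tables, "The full analysis set is defined as all randomized patients who received at least 1 dose of study drug" (SAP 6.2). Protocol 6.3.1 says that dosed patients who stop are not replaced.

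The outputs at issue state no other denominator:

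- SAP 8.7.2: "A summary of treatment emergent sodium findings will also be provided", in three categories (below 146, 146 to 150, above 150 mmol/L) at Weeks 6 and 12.
- SAP 8.7.3: "the number and percentage of subjects with at least 1 notable value will be tabulated by week and overall for Treatment period".
- SAP 8.6.4: the five Worst Itch Severity categories at each scheduled visit.
- SAP 8.6.4: "The proportion of patients with itching present at each body part will be presented at Week 12 and end of treatment", with the shift from baseline.

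Two further rules decide who can enter a numerator. SAP 8.1 admits only on-treatment values: within 2 days of the last dose for efficacy and 7 days for safety. SAP 7.3 maps an early-termination or unscheduled value to a planned visit only if it falls within 2 days of that visit.

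Protocol 8.7.3 has its own laboratory rule: "All laboratory evaluation summaries will include the patients in the Safety Population who have at least 1 postbaseline time point", and a baseline value as well for change criteria. The SAP does not repeat it, and SAP Section 9 does not list it among the changes. Protocol 8.1 says that where the two documents differ on analyses, "those found in the SAP will assume primacy".

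**The concern.** Once a patient has stopped, or has missed a sample or form, no later by-visit numerator can include that patient, but the denominator still does. The printed percentage then mixes two things: how often the finding occurs among those assessed, and how many were assessed. For continuous variables SAP 8.1 reports the number with non-missing observations. It specifies nothing equivalent for categorical ones.

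This matters most where a reader compares arms on a single row. If one dose loses more patients than placebo, its Week 12 rates of raised sodium, notable vital signs and residual itch all look lower for that reason alone. Protocol 4.3 names hypernatremia as a known effect in people with normal renal function, and the SAP gives sodium its own tables. The interim package (SAP 8.9.2.5) includes summaries of clinically important laboratory values and sodium findings, and the interim analysis is meant to identify safe doses. The documents do not say whether dosed patients who have not yet reached Week 6 or Week 12 would be in those interim tables. If they are, the fraction not assessed grows.

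**Working it through.** **The plan's own figures.** The documents give no expected rate for any of these outputs and no dropout or missing-visit rate. The usable planning figure is 60 patients per arm (SAP Section 5). Its stated power of 80% at effect size 0.52 reproduces (80.65% by the exact t calculation), but it does not depend on the denominator rule.

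**Formula.** Let p be the rate among assessed patients and m the fraction of the arm with no on-treatment value at that visit.

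- Shown rate = p × (1 − m)
- Absolute shortfall = p × m
- Relative shortfall = m

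**Range of m (assumed).**

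| Rate among assessed | m = 5% | m = 10% | m = 20% | m = 30% |
|---|---|---|---|---|
| 5% | 4.75% | 4.5% | 4.0% | 3.5% |
| 10% | 9.5% | 9.0% | 8.0% | 7.0% |
| 60% | 57% | 54% | 48% | 42% |

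**Two arms with equal rates, m = 10% on placebo and 25% on a dose (assumed).**

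- Itch present, 60% in both: 0.60 × 0.90 = 54% against 0.60 × 0.75 = 45%, a false difference of 9 points.
- Notable vital sign, 10% in both: 0.10 × 0.90 = 9.0% against 0.10 × 0.75 = 7.5%.
- A favourable category, such as severity None, 20% in both: 0.20 × 0.90 = 18% against 0.20 × 0.75 = 15%. Here the arm with more dropout looks worse.

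**A full category table.** Assume 60 dosed patients, of whom 45 have a Week 12 sodium value, split 40 / 4 / 1.

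- Dividing by 60 (SAP 8.1): 66.7%, 6.7%, 1.7%, which follow from counts totalling 45/60 = 75%.
- Dividing by 45 (assessed): 88.9%, 8.9%, 2.2%.

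The normal row shrinks in the same proportion as the abnormal rows.

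**What the protocol's laboratory rule would do.** In the same arm, assume that 3 of the 60 have no post-baseline laboratory value and 12 have Week 6 only. Sodium of 146 mmol/L or more at Week 12 is then:

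- 5/60 = 8.3% under SAP 8.1
- 5/57 = 8.8% under Protocol 8.7.3
- 5/45 = 11.1% among those assessed

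The protocol rule and the SAP default differ, but the protocol rule removes little of the by-visit shortfall.

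**The case against.** The case on the other side is substantial, and much of it limits the point.

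- **Unassessed patients are not scored as normal.** A reader might infer that they are counted as having no abnormality or no itch. No text does that. They fall in no category, as the sodium example shows. They act as non-events only if someone reads an abnormal row alone, or subtracts it from 100%.
- **The default is not universal.** SAP 8.2 uses other denominators for disposition, and the Week 12 NRS responder proportions come from imputed data.
- **Many rows are largely spared.** End of treatment uses the last non-missing on-treatment value. The highest sodium category attained and the overall notable vital-sign row use any on-treatment value, including unscheduled ones. Clinically important laboratory values are not specified by visit. The treatment comparison for body parts is at end of treatment. The sparing is not complete: an efficacy value must fall within 2 days of the last dose, while Protocol 6.3.1 lets the early-termination visit happen as soon as feasible.
- **The table templates are in a separate document** (SAP Section 1). They may show the number assessed or a missing row. That would soften the problem, but the SAP text would still set the denominator.
- **The interim reviewers see more than these rows.** Discontinuations with reasons, adverse events and patient listings are in the same package, and counts accompany percentages. The interim sodium summary is not stated to be by visit.
- **The protocol conflict is one of silence.** The SAP does not expressly revoke the laboratory restriction, and that restriction is not a by-visit denominator in any case.

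None of this supplies a denominator for the by-visit rows, so the default still governs them.

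**Conclusion.** The point holds for by-visit categorical summaries not based on imputed data. Following SAP 8.1 as it stands, each category percentage is too low, in relative terms, by exactly the fraction of the arm not assessed at that visit, and arms with unequal dropout are not comparable on those rows. The textual basis is firm. The size is unknown, because every value of m and p above is an assumption.

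Two limits on the inference should be kept in view. A reader might conclude that the understatement is always largest in the arm with most dropout. That is guaranteed only in relative terms: a 20% rate with 10% missing loses 2.0 points, while a 5% rate with 30% missing loses 1.5. Nor is the rate among assessed patients necessarily the rate in the whole arm. If missingness is related to outcome, a better denominator does not cure that, although it makes the gap visible.

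The harm is confined to descriptive tables. The primary analysis, the model-based tests and the conditional-power rule do not use these percentages. The correction is worth making before the tables are produced, but it is not critical to the trial's main conclusion.

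**What to change.** Add an exception to SAP 8.1 for by-visit and post-baseline categorical summaries of laboratory, vital-sign, ECG and patient-reported data that are not based on imputed data:

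- For by-visit rows, the denominator is the number of patients with a non-missing on-treatment value at that visit.
- For any-time rows, it is the number with at least one on-treatment value.
- Each table shows that number and the number missing, by arm.
- Adverse-event tables keep the population N.
- The interim tables follow the same rule.

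Reconcile the laboratory rule with Protocol 8.7.3, either by restating it in SAP 8.7.2 or by listing the departure in SAP Section 9.

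The cost is a short SAP edit and a denominator change in the table shells. The drawback is that denominators will vary by visit and some safety percentages will rise slightly.

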6.3 Removal of Patients from Therapy or Assessment

6.3.1 Discontinuation of Individual Patients

A patient may withdraw from the study at any time at his/her own request for any reason without prejudice to future medical care by the physician or at the institution. A patient may be withdrawn at any time due to the following reasons:

1. At the discretion of the Investigator or the Sponsor for safety, behavioral, compliance, or administrative reasons;
2. At the discretion of the Sponsor/Medical Monitor, if a patient receives a prohibited concomitant medication according to [Table 1 \(Section 6.4.7.2\)](#).

In addition, any patient who becomes pregnant during the Treatment Period or within 7 days after the last dose of study drug should be withdrawn from the study ([Section 6.5.2.6](#)).

Whenever possible, withdrawal of a patient from study drug by the Investigator should be discussed with the Medical Monitor before the patient stops study drug.

If study drug is discontinued, regardless of the reason, an Early Termination Visit should be completed after the last dose of study drug or, as soon as feasible. The Follow-up Visit is to be completed 7 to 10 days after the Early Termination Visit.

If study drug is discontinued, although a patient will not be obliged to give a reason for withdrawing prematurely, the Investigator must make a reasonable effort to obtain the reason while fully respecting the patient's rights. The reason(s) for termination and date of stopping study drug must be recorded on the electronic case report form (eCRF) and source documents.

If a patient discontinues early due to an adverse event, the event will be followed until resolution, the patient returns to baseline status, the condition stabilizes, or the patient is lost to follow-up.

If the patient withdraws consent for disclosure of future information, the Sponsor may retain and continue to use any data collected before such a withdrawal of consent.

Patients who discontinue after the administration of the first dose of study drug will not be replaced.

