6.4.5 Treatment Compliance

Treatment compliance with study drug will be assessed by study personnel via tablet counts of returned study drug and by questioning the patient, if necessary, at every visit, as applicable.

In addition, patients will be asked to record their daily intake of study drug.

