5 SAMPLE SIZE AND POWER

The minimum total sample size for this study is $N = 240$ patients (60 per treatment group) and the maximum is $N = 480$ (120 per treatment group). An unblinded interim analysis (IA) will be conducted when approximately 50-60% of the planned 240 patients have been randomized and have either completed the 12-week Treatment period or have discontinued study drug early. The primary goal of the IA is to identify dose(s) of oral CR845 that are both safe and efficacious. Doses that are found to be unsafe or poorly tolerated will be dropped from the study. No dose will be dropped for futility reasons. The details of sample size re-estimation based on conditional power are described in [section 8.9.1](#). A sample size of 60 patients per treatment group (the minimum sample size) will provide adequate power ($\geq 80\%$) for effect sizes ≥ 0.52 for a 5% type 1 error and a 2-sided T-test. Assuming a standard deviation of 2.6 for the primary efficacy variable, an effect size of 0.52 corresponds to a difference of approximately 1.4 point on a 0- to 10-point scale.

A sample size of 120 patients per treatment group (the maximum sample size) will provide adequate power ($\geq 80\%$) for effect sizes ≥ 0.40 for a 5% type 1 error and a 2-sided T-test. Assuming a standard deviation of 2.6 for the primary efficacy variable, an effect size of 0.40 corresponds to a difference of approximately 1 point on a 0- to 10-point scale. The power of a 2-sided hypothesis test with a 5% Type 1 error as a function of sample size and effect size is presented below.

Power as a Function of Effect Size (N = 120 Per Arm)^a

Effect Size	0.55	0.52	0.50	0.45	0.40	0.35
Power (N = 120)	98%	97%	97%	93%	86%	77%
Power (N = 60)	84%	80%	77%	68%	58%	47%

^a Power for a 2-sided T-test with equal variance and a 5% Type 1 error.

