7 STATISTICAL CONSIDERATIONS AND ANALYSIS

7.1 Derived Variables

The table below provides the list of derived variables for various duration derivations, drug compliance, baseline derivations and other important derivations applicable for this study.

Variables	Formula
Derivation of Duration	
Duration of treatment (days)	(Date of last dose of drug – date of first dose of study drug) + 1. (dates will be determined based on the patient daily dosing diary)
Duration of study (days)	(Date of study completion/discontinuation (for discontinued patients) – date of first dose) + 1
Study day	
 For dates before the date of first dose: Date of interest – date of first dose of study drug. For dates on or after the date of first dose: Date of interest – date of first dose of study drug + 1
Drug Compliance	
Compliance using accountability records	$[(\text{Sum of the total number of tablet dispensed across all visits} - \text{Sum of the total number of tablet returned across all visits}) / \text{Duration of treatment (days)}] * 100$
Compliance using daily dosing diary	$[(\text{Total number of tablet taken as per daily dosing diary}) / \text{Duration of study drug (days)}] * 100$
Baseline Derivations	
Baseline Worst Itching Intensity NRS score	The baseline score will be calculated as the average of the non-missing daily 24-hour Worst Itching Intensity NRS scores over the last 7 days prior to randomization; at least 4 completed Worst Itching Intensity NRS worksheets will be required prior to randomization.
Baseline (for other variables)	
 Time of assessment collected for the variable: baseline is defined as the last assessment prior to date/time of first dose of study drug whether scheduled or unscheduled. Time of assessment not collected for the variable: The baseline value is defined as the last observation prior to or on the date of the first dose of study drug whether scheduled or unscheduled
Change from baseline	Post baseline value – Baseline value

Statistical Analysis Plan (SAP)

Variables	Formula
Weekly Mean Worst Itching Intensity NRS score	

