8.6.2 Analysis of primary efficacy endpoint

The primary efficacy endpoint is defined as the change from baseline to week 12 of the Treatment period with respect to the weekly mean of the daily 24 hour Worst Itching Intensity NRS score. Testing of the primary efficacy endpoint will be 2-sided and conducted at the 5% error level.

The study will be considered positive if at least one safe and efficacious dose is identified. Effectiveness will be evaluated based on results of the primary efficacy analysis either using the estimate of treatment effect or the p-value of the hypothesis tests.

The null hypotheses H_{01} , H_{02} , H_{03} , and H_{04} given below will be tested against the alternative hypotheses H_{A1} , H_{A2} and H_{A3} respectively:

$$\begin{array}{llll} H_{01}: \mu_{D1} - \mu_P = 0, & H_{02}: \mu_{D2} - \mu_P = 0, & H_{03}: \mu_{D3} - \mu_P = 0, & H_{04}: \mu_{D123} - \mu_P = 0 \\ H_{A1}: \mu_{D1} - \mu_P \neq 0, & H_{A2}: \mu_{D2} - \mu_P \neq 0, & H_{A3}: \mu_{D3} - \mu_P \neq 0, & H_{A4}: \mu_{D123} - \mu_P \neq 0 \end{array}$$

Where μ_{D1} , μ_{D2} and μ_{D3} denote the mean change in Worst Itching Intensity NRS score from baseline to week 12 in the three active treatment dose groups and μ_P denotes the mean change from baseline to week 12 in the placebo group (placebo, P). D_1 denotes the CR845 0.25mg dose group, D_2 denotes the CR845 0.5mg dose group and D_3 denotes the CR845 1mg dose group and D_{123} denotes the doses (0.25, 0.5 and 1 mg) combined.

The weekly mean of the 24-hour Worst Itching Intensity NRS score will be defined as the sum of the daily Worst Itching Intensity NRS score reported during a specific week of the Treatment period (eg, Days 1 to 7, Days 8 to 14, Days 15 to 21, etc. till 78 to 84) divided by the number of non-missing scores for that week. If there are <4 non-missing daily worst itching scores during a specific week, the corresponding weekly mean worst itching score will be set to missing. The baseline score will be defined as the average of the daily 24-hour Worst Itching Intensity NRS scores over the last 7 days prior to randomization; at least 4 completed Worst Itching Intensity NRS worksheets will be required prior to randomization.

The primary efficacy variable will be analyzed using a mixed effects model with repeated measures (MMRM). The model will contain treatment, week, and treatment-by-week interaction as fixed effects; baseline score and renal disease status as covariates. For each

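### The SAP's two efficacy cut-offs (8.1 and 8.6) conflict, and under 8.1 a completer whose dosing diary stops before Day 79 has a measured Week 12 itch score set to missing and imputed

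*SAP*

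**What the plan says.** SAP 8.1 treats an efficacy assessment as on-treatment when it follows the first dose and falls "within 2 days from the last dose of study drug recorded in the patient diary". It adds: "Only on-treatment data will be used in summaries and statistical analyses", with the Patient Global Impression of Change (PGIC) as the only exception. For safety measures other than adverse events, 8.1 allows 7 days after the last dose but does not say where that date comes from.

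Wherever a source for the last-dose date is named, it is the diary. SAP 7.1, under duration of treatment, says "dates will be determined based on the patient daily dosing diary"; SAP 8.5.1 and Protocol 8.7.1 say the same for exposure. The missing-date rules in SAP 7.2.2 cover adverse events and medications only.

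SAP 8.6 gives a second efficacy cut-off. It uses data up to and including the date treatment was discontinued or completed, with no source for the date and no 2-day allowance.

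Other evidence on dosing is planned. Protocol 6.4.5 assesses compliance through "tablet counts of returned study drug and by questioning the patient", the latter if necessary. For patients who discontinue, Protocol 6.3.1 requires that the "date of stopping study drug must be recorded on the electronic case report form (eCRF"). The on-treatment definition uses neither.

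**The concern.** The drug diary is handed out with the tablets at each visit up to Day 70, so the last one covers roughly Days 70 to 84. The NRS scores are kept on worksheets and an assessment log (Protocol 6.5.1.1, SAP 7.3), and the Day 84 questionnaires are completed at the site. A patient can therefore take every tablet and supply every Week 12 outcome, yet have no dose recorded after about Day 70. Under 8.1 that gap in the record is handled as if treatment had stopped.

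The observed primary endpoint is then imputed in the main analysis and left out of Sensitivity analysis 1. Sensitivity analysis 2 fills such gaps according to the reason for discontinuing study drug, and a completer has none. The interim NRS analysis refers back to SAP 8.6.2, so it inherits the rule.

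Separately, 8.1 and 8.6 could lead two programmers to build different primary datasets from the same records. That needs settling however rare lost diaries turn out to be.

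**Working it through.** **The plan's own power figure.** The inputs are a two-sided 5% test ("Testing of the primary efficacy endpoint will be 2-sided and conducted at the 5% error level", SAP 8.6.2), 60 per arm ("A sample size of 60 patients per treatment group (the minimum sample size) will provide adequate power", SAP 5), effect size 0.52, and an SD of 2.6 ("Assuming a standard deviation of 2.6 for the primary efficacy variable", SAP 5). The difference is 0.52 × 2.6 = 1.352, which the plan rounds to 1.4. For a two-sample t-test, df = 2n − 2 = 118 and the noncentrality is d√(n/2) = 0.52 × √30 = 2.85. This gives 80.65% power against the stated 80%, so the figure is reproduced.

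**Day arithmetic.** Let L be the last day with a dose in the diary. The efficacy cut-off is L + 2 (SAP 8.1). The safety cut-off is L + 7 if L is also taken from the diary. Week 11 is Days 71 to 77 and Week 12 is Days 78 to 84; a weekly mean needs at least 4 scores (SAP 8.6.2). The final visit is Day 84 ± 2. Assume every NRS score was completed.

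| L | Efficacy cut-off | Week 11 scores kept | Week 12 scores kept | Week 12 mean | Day 84 questionnaires (not PGIC) | Day 84 laboratory, vital signs, ECG (cut-off L + 7) |
|---|---|---|---|---|---|---|
| 70 | 72 | 2 | 0 | missing | out | out (77) |
| 72 | 74 | 4 | 0 | missing | out | out (79) |
| 77 | 79 | 7 | 2 | missing | out | in (84) |
| 78 | 80 | 7 | 3 | missing | out | in (85) |
| 79 | 81 | 7 | 4 | kept | out | in (86) |
| 82 | 84 | 7 | 7 | kept | in | in (89) |
| 84 | 86 | 7 | 7 | kept | in | in (91) |

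The thresholds follow directly:
- Week 12 mean: L + 2 ≥ 81, so L ≥ 79.
- Day 84 questionnaires: L + 2 ≥ 84, so L ≥ 82.
- Day 84 safety values: L + 7 ≥ 84, so L ≥ 77.

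With L = 70, Week 11 is lost as well. If the Day 70 visit is held at Day 72 and L = 72, Week 11 survives but nothing from Week 12 does.

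**8.1 against 8.6.** Take a completer with L = 70 and treatment completed on Day 84. SAP 8.1 keeps data to Day 72; SAP 8.6, read alone, keeps them to Day 84. The difference can also run the other way. With a full diary to Day 84 and a final visit on Day 86, 8.1 keeps the questionnaires (84 + 2 = 86), while 8.6 drops them if completion means the last-dose date. If both rules must be met, the first patient still loses Week 12, and under that same meaning of completion the 2-day allowance has no effect.

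**Illustrative loss of power.** The documents give no rate of incomplete final diaries, so 2%, 5% and 10% are assumptions. Assume also that imputation recovers nothing, so the effective n is 60 × (1 − share lost).

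| Share losing Week 12 | Patients of 60 | Effective n | Power at 0.52 |
|---|---|---|---|
| 0% | 0 | 60 | 80.7% |
| 2% | 1.2 | 58.8 | 79.8% |
| 5% | 3 | 57 | 78.6% |
| 10% | 6 | 54 | 76.4% |

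**The case against.** The strongest reply is that the case is rare and mild. The rule looks at the last recorded dose, so earlier gaps do no harm, and one entry on or after Day 79 saves the Week 12 mean. Patients may be contacted to confirm daily dosing, and source data are verified. The patient stays in the Full Analysis Set, the imputation uses the patient's own earlier weekly scores, and the values remain in listings. Protocol 8.7.1 already dates the end of treatment from the diary, so the SAP is following the protocol. All of this stands, and it limits the size of the problem. It does not supply a fallback, and it does not reconcile 8.1 with 8.6.

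The remedy can also be questioned. The eCRF stop date is required only for discontinuers, and a tablet count gives a number, not a date. That is right: for completers these can support a completion date but cannot replace it.

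Nor do the documents say whether the drug diary and the NRS worksheets are returned together; SAP 9 itself calls the NRS record a patient diary. If both are lost, there is no measured Week 12 NRS score to discard. The site-completed questionnaires would still be dropped.

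A reader might infer more than the text allows:
- **That every Week 12 result is lost.** PGIC is exempt, and so are adverse events, which have their own rule.
- **That Week 12 laboratory results are lost by stated rule.** The safety sentence in 8.1 names no source. Their loss follows only if the diary date used for exposure is carried over.
- **That any incomplete final diary costs the primary endpoint.** Only one with nothing recorded from Day 79 onward does so, so applying 5% to 10% to all incomplete diaries would overstate the loss.
- **That the treatment comparison is biased.** Nothing in the documents suggests that diary loss differs by arm in this blinded trial.

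**Conclusion.** The point holds as a conflict between two cut-offs and a missing fallback. The loss of the Week 12 mean and of the three Day 84 questionnaires follows from 8.1 as written, at the Day 79 and Day 82 thresholds. Loss of Day 84 laboratory, vital-sign and ECG values is conditional on diary dating of the safety rule, at the Day 77 threshold.

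The effect is probably small. At the assumed 2% to 10%, the power cost is at most 0.9 to 4.3 percentage points (80.7 − 79.8 and 80.7 − 76.4), before any recovery by imputation. The case for change is that observed primary data would be discarded because of a gap in a different record, and that the analysis dataset is not uniquely defined.

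**What to change.** Put one last-dose definition in SAP 7.1, have 8.1 and 8.6 both refer to it for efficacy and safety, and state whether the 2-day allowance applies under 8.6. The order of sources would be:

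1. The diary date, when the diary is complete to the end of treatment.
2. Otherwise, for discontinuers, the eCRF date of stopping study drug.
3. Otherwise, for completers, the recorded treatment-completion date, when the tablet count or questioning of the patient is consistent with continued dosing. SAP 8.6 already relies on such a date; the SAP should name the field that holds it.

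Add that a missing diary page alone is not taken as stopped treatment. Settle the wording before unblinding, and report by arm how many patients needed a fallback.

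The cost is a change of SAP wording and a short derivation. The downside is that a few last-dose dates will be less exact than a diary entry.
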